5.4 SECONDARY ENDPOINT(S) ANALYSIS(SES)

The secondary objective for this study is the study partner's confidence in his or her ability to perform the injection and their perception of the ease of injection, as well as the study partner's satisfaction with and convenience of home administration. The corresponding endpoints consist of the responses to the caregiver part of the home administration questionnaire (HAQ) up to Week 52 (for the interim analysis) and up to Week 104 (for the primary analysis).

The home administration questionnaire is to be completed as per Schedule of Assessments at site visits on Weeks 36, 52, 76, 104, early termination and unscheduled visits, and comprises a caregiver and a participant portion. The Caregiver portion of the HAQ is the secondary endpoint of the study. The participant portion of the HAQ will be analyzed as an exploratory endpoint (Section 5.5.3).

The home administration questionnaire comprises 4 items to be completed by study partner and 2 items to be completed by participants. The Caregiver portion of the questionnaire includes confidence with administration, convenience, ease of use, and overall satisfaction. Each item is rated on a 4-point verbal Likert scale and respondents will be asked to consider their most recent at home administration. Participants will complete satisfaction and convenience items with the same response options and recall period. Responses to this questionnaire may be captured electronically and transferred to the database directly from the core laboratory.

Descriptive summaries will be reported separately for each of the 4 items of the caregiver portion of the HAQ on the H-SE analysis set. Responses to each item are considered ordinal data: for each item and at each visit, the number of available

responses as well as the number and percentage for each response category will be reported. No imputation of missing data will be performed for this endpoint.

Descriptive tables will summarize the number of home administrations by study partner per participant as well as the reasons for the study partner not performing home-administrations. Reasons for switches in the person administering the study drug will be summarized as well. Graphical representations may be used to show the proportion of participants receiving administrations at home by study partner over time or to visualize the administrations by their study partner vs by a healthcare professional at home or at the site over time. The change from baseline in amyloid burden will be summarized as described in Sections 5.3.5.1 and 5.3.3 for participants who have had at least one home administration by their study partner vs those who have had none. These tables and figures will be based on the SE analysis set.

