4. ANALYSIS SETS

The following analysis sets are defined:

Analysis Set	Definition
Intent to treat (ITT)	All enrolled participants (i.e., who gave informed consent, did not fail screening, and had at least one Amyloid PET scan with a valid quantitative measurement performed with either florbetaben or flutemetamol), whether or not the participant received the assigned treatment.
Safety-evaluable (SE)	All participants enrolled who received at least one dose of study treatment, whether prematurely withdrawn from the study or not.
MRI safety-evaluable (M-SE)	All participants of the SE analysis set who had at least one post-baseline MRI assessment.
Amyloid-PET-longitudinal	All participants in the ITT analysis set with a valid post-baseline quantitative amyloid PET measurement performed with either florbetaben or flutemetamol.
MRI modified intent-to-treat (MRI-mITT)	All participants in the ITT analysis set who had at least one valid volumetric MRI quantitative measurement.
MRI-longitudinal	All participants in the MRI-mITT with at least one valid post-baseline volumetric MRI quantitative measurement.

Opportunity for home dosing safety-evaluable (OH-SE)	All participants of the SE analysis set who did not discontinue study drug before week 26.
Home dosing by study partner safety-evaluable (H-SE)	All participants of the SE analysis set who received at least one dose of study treatment administered at home by caregiver / study partner.

ITT = intent to treat; H-SE = safety-evaluable with home dosing by study partner; M-SE = safety-evaluable with post-baseline MRI; MRI = magnetic resonance imaging; MRI-mITT = modified intent-to-treat with at least one valid vMRI measurement; OH-SE = safety evaluable with opportunity for home dosing by study partner; SE = safety-evaluable;.

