5.1.1 Visit Windowing

The analysis of data will be undertaken using reporting windows. As all the endpoints in the study are collected at different time frequencies, different sets of reporting windows will be applied depending on the frequency of assessments. In case of more than one assessment within a time window, the assessment with the date closest to the target (scheduled) day will be selected.

For amyloid PET assessments, time windows will be used ([Table 2](#)). Because of visit windowing, data collected at an early termination visit will be summarized at the appropriate time in the trial. For participants who have discontinued treatment early, if a PET scan is performed more than 56 days after the date of last dose, the PET scan will not be used for the analysis.

Table 2 Time Windows for Amyloid PET Endpoints

Visit	Target study day	Time window
Baseline	1	Up to day 1
Week 52	365	281, 449
Week 104	729	645, 813

For endpoints of home administration questionnaire (Caregiver or Patient), time windows will be applied ([Table 3](#)).

Table 3 Time Windows for Home Administration Questionnaire Endpoints

Visit	Target study day	Time window
Baseline	- (no baseline assessment planned)	- (no baseline assessment planned)
Week 36	253	2, 308
Week 52	365	309, 448
Week 76	533	449, 630
Week 104	729	631, 770

For cognitive and functional endpoints, time windows will be applied ([Table 4](#))

Table 4 Time Windows for Cognitive and Functional Endpoints

Visit	Target study day	Time window
Baseline	1	Up to Day 1
Week 24	169	2, 266
Week 52	365	267, 448
Week 76	533	449, 630
Week 104	729	631, 770

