5.6.8 Safety of Home Administration by the Study Partner

Descriptive analyses will be performed to assess the safety of home administrations of study drug by the study partner. These will compare data at a participant level and at an injection level.

Participant Level

On the participant level, a descriptive table will show:

- Number and frequency of participants with at least one home administration by study partner
- Number and frequency of participants who changed the study partner during the study (overall)
- Number and frequency of participants with different overall number of changes in study partner
- Total number of home administrations by study partner per participant (descriptive statistics)
- Percentage of possible home administrations by study partner (i.e., number of actual home administrations by study partner divided by maximum possible number) per participant (descriptive statistics)
- Percentage of participants who received home administration by study partner at each visit (starting from Week 26, excluding planned in-clinic visits; line plot)
- First week with home administration by study partner
- Heat map of administrations by study partner or HCP at home or at site

The summaries above will be presented for the SE, OH-SE, and/or the H-SE analysis set as appropriate.

Furthermore, participants will be grouped in the following way:

- Participants who have had no home administrations by their study partner
- Participants who have been dosed at home by their study partner at least once

The threshold of 1 home administration by study partner may be varied for additional exploratory, data-driven analyses.

For these two groups, demographic data and baseline characteristics will be summarized as described in Section 5.7.2. Furthermore, demographics and characteristics of all study partners will be summarized.

An AE overview table will summarize the AE profile by group. Selected AE tables of ISRs, systemic injection reactions, and hypersensitivity will provide the frequency of these events by group. Additionally, medication errors will also be summarized descriptively by group.

Injection Level

On the injection level, each single injection of study drug from Week 26 onwards (after the scheduled training of study partners at the site) will be grouped in the following way:

- Home administration by study partner

Gantenerumab—F. Hoffmann-La Roche Ltd

Statistical Analysis Plan: WN29722 (GRADUATION)

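### The caregiver questionnaire is summarised on an ever-dosed-at-home set with no date rule, so answers given before a study partner's first home injection can count as ratings of home dosing

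*SAP*

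**What the plan says.** SAP Section 5.4 makes the caregiver HAQ items the secondary endpoint: confidence, convenience, ease of use and overall satisfaction. "Descriptive summaries will be reported separately for each of the 4 items of the caregiver portion of the HAQ on the H-SE analysis set". SAP Section 4 defines H-SE as participants in the safety-evaluable set "who received at least one dose of study treatment administered at home by caregiver / study partner". The definition has no date condition and does not require home dosing to continue.

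The HAQ is completed at "site visits on Weeks 36, 52, 76, 104, early termination and unscheduled visits". Neither Section 5.4 nor the protocol's schedule of activities makes completion depend on a home dose having been given. On content, "respondents will be asked to consider their most recent at home administration".

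For each item and visit the SAP reports the number of available "responses as well as the number and percentage for each response category will be reported", and adds: "No imputation of missing data will be performed for this endpoint". The denominator of the percentages is not stated; available answers is the natural reading.

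On timing, SAP Section 5.1.1 states: "For endpoints of home administration questionnaire (Caregiver or Patient), time windows will be applied". Its Table 3 assigns Days 2 to 308 to Week 36, with target Day 253. If a window holds several assessments, the one closest to the target day is used.

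**The concern.** The endpoint is meant to describe how caregivers who inject at home experience doing so. Restricting it to H-SE signals that answers without home experience should be left out. But H-SE selects people, not answers. Once a partner has given one home dose at any point, every answer from that caregiver qualifies, including answers given before that dose.

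Week 36 is the most exposed visit. It is the first scheduled HAQ, it comes soon after home dosing becomes possible, and home dosing is optional with no fixed start. Under SAP Table 1 the interim analysis covers the HAQ up to Week 52, so Week 36 is one of its two scheduled HAQ visits. SAP Section 5.8.1 says the interim analysis is to support a potential filing. With a single arm, no comparison group would reveal or offset a mixture of answers given with and without home experience.

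A second, smaller matter is that a table of available answers does not show who is missing at later visits.

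**Working it through.** The plan states no sample size or precision for the HAQ, so there is no figure to reproduce. The check covers the timing rules and then gives an illustration.

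**1. Timing convention.** Target day = 7 × week + 1. Week 36: 7 × 36 + 1 = 253. Week 52: 365. Week 76: 533. Week 104: 729. All four agree with SAP Table 3.

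**2. Earliest partner home dose.** Under Protocol Section 4.3.2.1 the partner observes the first three doses and injects under supervision at Weeks 12, 16, 20 and 24; home dosing may follow. SAP Section 5.6.8 starts its injection-level grouping at Week 26, nominally Day 7 × 26 + 1 = 183. A scheduled Week 36 answer is therefore preceded by at most five home-eligible doses (Weeks 26, 28, 30, 32 and 34).

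**3. Does the start vary?** The SAP expects it to: Section 5.6.8 tabulates the first week with a partner home administration. A caregiver whose first home dose falls after Week 36 is in H-SE and has a scheduled Week 36 HAQ, and no rule removes that answer. The same logic applies at later visits to anyone starting later still.

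**4. The window.** Week 36 spans 308 − 2 + 1 = 307 days, of which 183 − 2 = 181 (59%) precede Day 183. Before Week 36 the schedule marks the HAQ only under unscheduled visits. Because the answer closest to Day 253 is used, an early one counts only if it is the sole answer in the window.

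**5. Caregivers who stop.** Protocol Section 4.3.2.1 lets dosing pass to a nurse or study staff. The caregiver then remains in H-SE and the HAQ stays scheduled. After treatment withdrawal, Protocol Sections 4.6.5 and 4.7.1 list safety, PD, cognition and function for return visits. The HAQ is not named there, although it is collected at the early termination visit.

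**6. Illustration of size (all inputs assumed).**

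- *Early answers at Week 36.* Let q be the share of answers preceding the first home dose, p the favourable share among them, and 90% the favourable share among the rest. Reported = 0.90 × (1 − q) + p × q. With q = 5%, p = 70%: 0.855 + 0.035 = 89%. With q = 30%, p = 50%: 0.63 + 0.15 = 78%. If p is also 90%, nothing changes.
- *Missing answers later.* Suppose a share s stop and none answers, 90% of the others are favourable, and 30% to 50% of the stoppers would have been. The table shows 90%. Had all answered, the figure would be 0.90 × (1 − s) + (0.30 to 0.50) × s:

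| s | Had all answered |
|---|---|
| 10% | 84% to 86% |
| 20% | 78% to 82% |
| 35% | 69% to 76% |

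If every stopper answers, the available-answer figure equals the all-H-SE figure.

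**The case against.** The strongest reply is that the analysis is descriptive, tests no hypothesis, and already discloses much of this. The number of answers is given per item and visit. Section 5.4 tabulates, on the safety-evaluable set, reasons for partners not dosing at home and for changes of administrator. Section 5.6.8 adds the first home-dosing week, the percentage dosed at home by the partner at each visit, and a heat map. Section 5.1 promises missing-data counts for key endpoints. The item wording may itself deter caregivers with no home dose to rate, and the form may have a skip option that these documents do not show.

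Most of that stands as mitigation, but it does not close the gap. Those tables are not linked to individual answers, the HAQ is not named among the key endpoints, and an instruction to respondents is not an exclusion rule in the analysis.

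The objection does defeat three stronger readings that a reader might draw:

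- *That caregivers who stop injecting are removed from the denominator.* They are not; H-SE keeps them and they are still scheduled to answer.
- *That the Day 2 window start lets many early answers in.* Such an answer must be unscheduled, the only one in the window, and from someone who doses at home later.
- *That caregivers who hand over to a nurse are rating the nurse's injection.* The reference dose is not tied to an injector, but the items include the caregiver's own confidence and ease of use, and the form is not available to settle it.

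**Conclusion.** The point holds in a limited form. As written, the only secondary endpoint can include answers that precede any home injection by the study partner, because H-SE membership is not dated against the answer. This follows from the text and needs no assumption.

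How many answers are affected cannot be determined from the documents. The 78% to 89% range rests wholly on assumed shares, and even its direction depends on whether inexperienced caregivers answer less favourably. The missing-answer figures are likewise assumed. The documents' only 35% is a sample-size allowance for drop-out, discontinuation and standard-deviation uncertainty together, so it should not be read as an expected HAQ loss.

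Loss of caregivers from later percentages is real only where no answer is recorded, mainly after treatment withdrawal, and even then one early-termination answer is collected. This is a minor point that is cheap to repair and does not touch the primary endpoint.

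**What to change.** Amend SAP Section 5.4 as follows:

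- Include a caregiver answer only if the administration record shows at least one home dose by the study partner on or before the date of the answer. Show earlier answers separately.
- Use this rule in place of moving the start of the Week 36 window to Day 183. With the ±3-day window for Q2W doses, a Week 26 home dose can fall on Day 180, so a fixed cut would be inexact. It would also miss caregivers who start after Week 36.
- State that percentages use available answers.
- For each visit, add the H-SE total with the numbers still dosing at home, stopped home dosing, and with no answer.
- Keep answers from caregivers who have stopped, and flag them. Requiring a home dose since the previous questionnaire would remove caregivers who stopped or were temporarily interrupted, and those who stopped may be the less satisfied.

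The cost is SAP wording and one merge with administration records that Section 5.6.8 already needs. The downside is slightly fewer answers at Week 36.

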5.5 EXPLORATORY ENDPOINT(S) ANALYSIS(SES)

The change from baseline in the continuous, exploratory endpoints listed below.

5.5.1 Amyloid PET Comparison to Data from GRADUATE I and GRADUATE II

The feasibility of using amyloid PET data from the pivotal ongoing GRADUATE I and GRADUATE II as an external control group will be explored for a comparison of measured amyloid reduction between dosing regimens. Such an analysis may be performed at the primary analysis of this study.

In case that it is feasible to compare the change from baseline to Week 52 and to Week 104 in deposited amyloid as measured by brain amyloid PET within this study with the change measured in GRADUATE I and GRADUATE II as external control, then this analysis will be reported separately. Pertinent descriptions of the planned analysis will be appended to this SAP as a separate document.

5.5.2 Clinical Efficacy Outcomes

Clinical efficacy outcomes of CDR-SOB, MMSE, ADAS-Cog, Verbal Fluency Task, Coding, and ADCS-ADL will be assessed and collected via electronic tablets. The number of participants with available results at each visit will be presented. For all these outcomes, the total score, the change and percent change from baseline (if applicable) will be summarized descriptively for all participants at each visit.

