3. SAMPLE SIZE DETERMINATION

Determination of sample size is relative to the sample of participants assessed by amyloid PET imaging using florbetaben. The sample size for this study is determined as the number of participants needed for the estimated change from baseline to Week 104 in amyloid PET load to fall into a 10 CL confidence interval (CI) around its true value. With a standard deviation of 25.67 CL (see below), 150 participants are required to fulfill this criterion. However, due to a lower than expected screen failure rate at the end of the enrollment period, a total of 192 participants have been enrolled.

The standard deviation of amyloid reduction was estimated using amyloid PET data from the ongoing Studies WN25203 (hereafter referred to as “SCarlet RoAD”) and WN28745 (hereafter referred to as “Marguerite RoAD”) open label extension (OLE) periods (based on a cutoff date of 14 October 2019), yielding a value of 25.67 CL.

Uncertainties of the parameters affecting the estimation (e.g., drop-out rate, study drug discontinuation rate, and standard deviation) were assumed to be equivalent to a decrease in sample size of up to around 35% and were corrected for accordingly. This drop-out rate is calculated based on Marguerite RoAD OLE at Week 104 that was ongoing at the time the study protocol was written. A sample size increase may be considered if factors external to the study would warrant a change to the sample size assumption.

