5.1 GENERAL CONSIDERATION

In the following sections, for all continuous variables for which descriptive statistics are indicated, the following statistics will be reported: the number of observations, the mean, median, standard deviation, and minimum and maximum. The 25th and 75th percentiles (Q1 and Q3) will also be reported for selected tables. Descriptive summaries of discrete data will include frequencies expressed in terms of number and percentage of participants.

For safety endpoints, the baseline is defined as the last available assessment prior to first study drug intake. For all other assessments, the baseline is defined as the last available assessment before or on the day of first study drug intake, unless specified otherwise.

All PD analyses and all clinical efficacy analyses will be performed on the ITT analysis set, unless specified otherwise. Safety analyses will be performed on the SE analysis set, except for analyses of MRI findings which will be performed on the M-SE analysis set and analyses of home administrations by study partner that will be performed on the SE, OH-SE, or H-SE analysis sets, as appropriate.

All analyses will be purely descriptive or exploratory without any formal hypothesis testing. For exploratory tests, a two-sided significance level of 5% will be used.

In general, missing outcome data will not be replaced or imputed unless specified otherwise. Number and percentage of missing data points will be reported for each visit for key endpoints of interest.

In statistical models using change from baseline of a given outcome measure as the dependent variable, participants with missing baseline outcome measure will be

Gantenerumab—F. Hoffmann-La Roche Ltd

Statistical Analysis Plan: WN29722 (GRADUATION)

18

Clinical Study Report: gantenerumab - F. Hoffmann-La Roche Ltd

Protocol Number: WN29722

Report Number: 1117435

18

excluded from the analysis. There will be no imputation of baseline value for outcome measures.

The impact of the COVID-19 pandemic on the study and its conduct will be monitored and the overall impact will be assessed and described in the Clinical Study Report.

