5.3.3 Main Analytical Approach for Primary Endpoint

Descriptive summary statistics for the brain amyloid CL load at baseline, Week 52 and Week 104 as well as the change from baseline to Week 52 and to Week 104 will be produced on both the ITT and Amyloid-PET-longitudinal analysis sets. Descriptive summaries of the primary endpoint will present the mean, standard deviation, median, and minimum and maximum.

A Mixed Model for Repeated Measures (MMRM) analysis will be used to estimate the mean change in CL from baseline to Week 52 and to Week 104 on the ITT analysis set. The model will include the change from baseline in CL as the dependent variable, while adjusting for visit (as categorical), apolipoprotein E allele $\epsilon 4$ (APOE $\epsilon 4$) status (as categorical; carrier vs non-carrier), baseline CL, and baseline CL-by-visit. Visit will be treated as the repeated variable within a participant. An unstructured variance-covariance matrix will be applied to model the within-participant errors; in the case of non-convergence, compound symmetry will be used, together with a robust estimator of standard error ("sandwich" estimator).

In line with the primary estimand definition, data acquired after the ICE "Substantial reduction in drug exposure due to the COVID-19 pandemic" (as defined above) or more than 56 days from date of last dose will be excluded from the analysis and treated as missing for the primary analysis purposes.

There will be no data imputation for missing data. However, the MMRM model provides unbiased estimates and valid inference in the presence of missing data, under the MAR (missing at random) assumption.

The least squares means at Week 52 and at Week 104 will be estimated and presented with a 95% CI.

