5.5.4 Biomarker Analyses

5.5.4.1 Volumetric MRI Analyses

Analysis of volumetric MRI will be based on the MRI-mITT analysis set.

Volumetric MRI, for each brain region, will be summarized visit using descriptive statistics for the absolute volume at baseline and percent change from baseline at post-baseline visits. These summaries will be provided for both the MRI-mITT and the MRI-longitudinal analysis sets.

A MMRM analysis will be used to estimate the mean percent change from baseline to Week 104 (as well Week 48) in volumetric MRI for each brain region. The model will include the percent change from baseline in volumetric MRI as the dependent variable, while adjusting for visit (as categorical), baseline age, gender (as categorical), APOE ε4 status (as categorical; carrier vs. non-carrier) and disease stage (as categorical). Visit will be treated as the repeated variable within a participant. An unstructured variance-covariance matrix will be applied to model the within-participant errors; in the case of non-convergence, compound symmetry will be used, together with a robust estimator of standard error (“sandwich” estimator).

There will be no data imputation for missing data. However, the MMRM provides unbiased estimates and valid inference in the presence of missing data, under the MAR (missing at random) assumption.

The following brain regions will be considered:

- Whole brain volume
- Regional brain volumes
- Ventricular volume

Other exploratory analyses based on other brain regions may be reported separately.

In addition, exploratory biomarker analysis will be performed to assess change from baseline to Week 104 in functional brain connectivity, fiber tract integrity, and cerebral blood perfusion.

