5.5.4.2 Plasma Biomarker Analyses

Exploratory fluid plasma biomarkers will be assessed at each visit for tau and amyloid pathology as well as neurodegeneration, including, but not limited to, the following:

- p-tau
- A β 1-42
- Neurofilament light chain (NFL)
- Glial fibrillary acidic protein (GFAP)

The plasma concentration of these biomarkers will be assessed. Analysis of plasma biomarkers will be based on the ITT analysis set. Biomarker data will be summarized for each assessment visit using descriptive statistics of absolute values as well as change from baseline values.

An MMRM analysis will be used to estimate the mean change from baseline to Week 104 (but also to Week 24, 36, 52, and 76) for each plasma biomarker. The model will include the change from baseline in the plasma biomarker as the dependent variable, while adjusting for visit (as categorical), APOE ϵ 4 status (as categorical; carrier vs non-carrier), baseline biomarker and baseline biomarker-by-visit. Visit will be treated as the repeated variable within a participant. An unstructured variance-covariance matrix will be applied to model the within-participant errors; in case of non-convergence, compound symmetry will be used, together with a robust estimator of standard error ("sandwich" estimator). The MMRM model will be based on log-transformed biomarker data.

There will be no data imputation for missing data. However, the MMRM provides unbiased estimates and valid inference in the presence of missing data, under the MAR (missing at random) assumption.

Other exploratory plasma biomarkers may be reported separately.

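### Week 104 cognition and function are estimated only from participants with a score in that window, so decline is understated if those who worsen are more often missing; an MMRM already in the SAP would use the earlier scores

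*SAP*

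**What the plan says.** SAP Table 1 lists change from baseline to Week 104 in CDR-SOB, MMSE, ADAS-Cog11, ADAS-Cog13, Verbal Fluency, Coding and ADCS-ADL as exploratory endpoints of the primary analysis. SAP 5.5.2 gives their whole analysis: "The number of participants with available results at each visit will be presented", and "the total score, the change and percent change from baseline (if applicable) will be summarized descriptively for all participants at each visit". The general rule in SAP 5.1 is that "In general, missing outcome data will not be replaced or imputed unless specified otherwise", and nothing else is specified for these scales. SAP 5.1 also states that "All PD analyses and all clinical efficacy analyses will be performed on the ITT analysis set".

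Other outcomes are handled differently:

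- PET (SAP 5.3.3): "A Mixed Model for Repeated Measures (MMRM) analysis will be used to estimate the mean change in CL from baseline".
- Volumetric MRI (SAP 5.5.4.1): "A MMRM analysis will be used to estimate the mean percent change from baseline to Week 104".
- Plasma biomarkers (SAP 5.5.4.2): "An MMRM analysis will be used to estimate the mean change from baseline to Week 104".

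In all three sections the SAP justifies the model by its validity under missing at random (MAR). Protocol 6.8 allowed either descriptive statistics or models for the exploratory endpoints and left the detail to the SAP.

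**The concern.** A by-visit mean uses only participants who have a value in that window. Naming the ITT set does not change this, because a participant without a Week 104 score contributes nothing to the Week 104 mean. SAP Table 4 defines windows at Weeks 24, 52, 76 and 104, so a participant who leaves after Week 52 or 76 can already have shown decline. That information appears in the earlier visit summaries but does not enter the Week 104 estimate.

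Exploratory status does not explain the difference, since volumetric MRI and plasma biomarkers are exploratory too. For PET, the analysis restricted to participants with data at the visit is only supplementary to the MMRM (SAP 5.3.5). For cognition and function, its equivalent is the only analysis.

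At stake is how the reported two-year decline is read. In a single-arm study there is no concurrent group to show how much of a favourable Week 104 mean reflects who remained, and the plan gives no second estimate to set beside it.

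**Working it through.** **No figure to reproduce.** The documents give no SD, expected decline or missing-data rate for any cognitive or functional scale.

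**Inputs from the documents.** 192 enrolled (SAP 3); post-baseline visits at Weeks 24, 52, 76 and 104 (SAP Table 4); and, for PET sizing, uncertainty "assumed to be equivalent to a decrease in sample size of up to around 35" percent (SAP 3). That last figure combines drop-out, drug discontinuation and SD uncertainty, so it serves only as the upper end of a range.

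**Assumptions not in the documents.** Change is oriented so that positive means worse. Week 104 change has SD 1 and true mean 0.6. Between-visit correlations are 0.21 to 0.64. Missing at Week 104: 15%, 25% or 35%, by monotone drop-out. The odds ratio (OR) of leaving is 1, 1.5, 2 or 3 per SD of worsening. Every simulated participant has a Week 24 score.

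**Direction.** With share missing *d*:

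bias = −*d* × (mean worsening of the missing − mean worsening of the observed)

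This is negative whenever those missing worsened more. With *d* = 0.35 and a gap of 0.5 SD, bias = −0.35 × 0.5 = −0.175 SD.

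**Size.** One million simulated participants per scenario. The observed-case Week 104 mean was compared with a likelihood-based mean under an unstructured covariance, fitted by sequential regression on earlier visits (the one-arm MMRM equivalent, without baseline or APOE ε4 terms).

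Leaving depends on the last observed score (MAR):

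| Missing | OR 1.5 | OR 2 | OR 3 | MMRM |
|---|---|---|---|---|
| 15% | −0.030 (−5%) | −0.052 (−9%) | −0.077 (−13%) | about 0 |
| 25% | −0.052 (−9%) | −0.088 (−15%) | −0.130 (−22%) | about 0 |
| 35% | −0.077 (−13%) | −0.127 (−21%) | −0.182 (−30%) | about 0 |

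The OR columns show the bias of the observed-case mean in SD units, with the percentage of the true decline in brackets.

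Leaving depends on the unseen current score (missing not at random, MNAR); observed-case bias, then MMRM bias:

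| Missing | OR 1.5 | OR 2 | OR 3 |
|---|---|---|---|
| 15% | −8%, −5% | −13%, −8% | −19%, −12% |
| 25% | −13%, −8% | −21%, −14% | −31%, −20% |
| 35% | −19%, −12% | −31%, −20% | −44%, −30% |

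At 35% and OR 2 the MNAR biases are −0.185 and −0.119 SD, so the MMRM removes (0.185 − 0.119)/0.185 = 36% of the bias. With OR 1, both estimators are unbiased at every level of missingness.

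**At the trial's size.** With N = 192, 35% missing and OR 2 under MAR (400 replicates), the mean estimates are 0.466 observed-case, 0.595 MMRM and 0.597 with complete data. The sampling SDs are 0.094 for observed-case and 0.092 for MMRM. The observed-case shortfall against complete data, 0.597 − 0.466 = 0.131, exceeds its own sampling SD, and the model costs no precision here.

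**The case against.** The strongest reply is that a descriptive analysis was a permitted choice. Protocol 6.8 names it as an option, protocol 3.3.3 makes these endpoints exploratory only, and SAP 2 tests no hypotheses. A single-arm cognitive mean cannot show benefit, whether it is observed-case or model-based. All of this stands, and it limits the point to an improvement in how decline is estimated.

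The plan also limits the problem:

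- Protocol 4.6.5 and 4.7.1 ask participants who stop treatment to return for cognition and function.
- The early-termination visit collects every scale (protocol Appendix 1, Table 4), and a score between days 631 and 770 counts as Week 104.
- Available numbers are shown per visit, and SAP 5.7.1 tabulates the reasons for discontinuation and its distribution by visit.

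Attrition will therefore be visible and may be modest. But visible counts do not correct the mean.

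A reader might infer three stronger things that the documents do not support:

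- **That earlier scores are discarded.** They are summarised at their own visits; they are only unused for Week 104. The documents also do not say how many leavers will have earlier scores.
- **That 35% of Week 104 scores will be missing.** The figure was set for PET, mixes several uncertainties and is an upper bound.
- **That an MMRM cures the problem.** Its near-zero bias holds under MAR, the condition imposed in the first table. The second table shows what remains otherwise.

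**Conclusion.** The point holds as a conditional one. The Week 104 change in cognition and function is an observed-case estimate, and it understates decline if those who worsen are more often missing. The documents do not show that they are, so it would be wrong to conclude that the reported decline will be biased.

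Under the assumed inputs, the understatement is about 5–30% of the true decline under MAR, and an MMRM removes it. Under MNAR, at 35% missing and OR 2, the MMRM reduces it from about 31% to about 20%. The direction follows from the condition; the size rests on the assumptions and could be smaller if most treatment stoppers return.

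The contrast with MRI is limited to volumetric MRI: SAP 5.5.4.1 specifies no model for connectivity, fiber-tract or perfusion measures. No primary conclusion changes, because these endpoints are exploratory and untested. The change is worth making because it is cheap and uses data already scheduled.

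**What to change.** In SAP 5.5.2, for each scale:

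1. Add the plasma-biomarker MMRM on untransformed change from baseline: visit, baseline, baseline-by-visit and APOE ε4 status, unstructured covariance, all visits to Week 104.
2. Report the Week 104 mean change with a 95% CI, and state that it relies on MAR.
3. State whether scores collected after treatment discontinuation are included. The 56-day rule in SAP 5.1.1 and 5.3.3 is written for PET, and nothing equivalent is given for these scales.
4. Keep the by-visit tables, labelled as observed-case.

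The cost is SAP wording, reuse of code already needed for plasma, and a model estimate for each of seven scores. No new visits or data are required. The downsides are a few more outputs, possibly a slightly larger reported decline, and reliance on MAR.
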